**Table 2-4 CTCAE grades for laboratory parameters to be analyzed**

CTCAE v4.03 Term	Grade 1	Grade 2	Grade 3	Grade 4
HGB decreased (Anemia)	<LLN – 100 g/L	<100 – 80 g/L	<80 g/L	Life-threatening consequences; urgent intervention
Platelet count Decreased	<LLN – 75.0 x10e9 /L	<75.0 – 50.0 x10e9 /L	<50.0 – 25.0 x10e9 /L	<25.0 x 10e9 /L
White blood cell decreased	<LLN - 3.0 x 10e9 /L	<3.0 - 2.0 x 10e9 /L	<2.0 - 1.0 x 10e9 /L	<1.0 x 10e9 /L
Neutrophil count decreased	<LLN - 1.5 x 10e9 /L	<1.5 - 1.0 x 10e9 /L	<1.0 - 0.5 x 10e9 /L	<0.5 x 10e9 /L
Lymphocyte count decreased	<LLN - 0.8 x 10e9/L	<0.8 - 0.5 x 10e9 /L	<0.5 - 0.2 x 10e9 /L	<0.2 x 10e9 /L
Creatinine increased	>ULN - 1.5 x ULN	>1.5 - 3.0 x ULN	>3.0 - 6.0 x ULN	>6.0 x ULN
TBL increased	>ULN - 1.5 x ULN	>1.5 - 3.0 x ULN	>3.0 - 10.0 x ULN	>10.0 x ULN
GGT increased	>ULN - 2.5 x ULN	>2.5 - 5.0 x ULN	>5.0 - 20.0 x ULN	>20.0 x ULN
ALT increased	>ULN - 3.0 x ULN	>3.0 - 5.0 x ULN	>5.0 - 20.0 x ULN	>20.0 x ULN
AST increased	>ULN - 3.0 x ULN	>3.0 - 5.0 x ULN	>5.0 - 20.0 x ULN	>20.0 x ULN
ALP increased	>ULN - 2.5 x ULN	>2.5 - 5.0 x ULN	>5.0 - 20.0 x ULN	>20.0 x ULN

Shift tables will be presented comparing baseline laboratory result (CTCAE grade) with the worst results (expressed in CTCAE grade) during the treatment period analyzed.

The number and percentage of subjects with newly occurring liver enzyme abnormalities will also be summarized based on the event criteria given in [Table 2-5](#).

**Table 2-5 Liver-related events**

Parameter	Criterion
ALT	>3xULN; >5xULN; >8xULN; >10xULN, >20xULN
AST	>3xULN; >5xULN; >8xULN; >10xULN; >20xULN
ALT or AST	>3xULN; >5xULN; >8xULN; >10xULN; >20xULN
TBL	>1xULN; >1.5xULN; >2xULN; >3xULN,
ALP	>1.5xULN; >2xULN; >3xULN; >5xULN
ALT or AST & TBL	ALT or AST >3xULN & TBL >1.5xULN; ALT or AST >3xULN & TBL >2xULN; ALT or AST >5xULN & TBL >2xULN; ALT or AST >8xULN & TBL >2xULN; ALT or AST >10xULN & TBL >2xULN; ALT or AST >20xULN & TBL >2xULN;
ALP & TBL	ALP >3xULN & TBL >2xULN ALP >5xULN & TBL >2xULN
ALT or AST & TBL & ALP	ALT or AST >3xULN & TBL >2xULN & ALP <2xULN (Potential Hy's Law) Note: elevated ALP may suggest obstruction as a consequence of gall bladder or bile duct disease; ALP may also be increased in malignancy. FDA therefore terms Hy's Law cases as indicators of pure hepatocellular injury . This does not mean that cases of ALT or AST >3xULN & TBL >2xULN & ALP >2xULN may not result in severe DILI. ALT or AST >3xULN & TBL >2xULN & ALP <2xULN (Potential Hy's Law) or reported Hy's Law case Note: "Hy's Law case" is a lower level term in MedDRA (10070546) and may be reported as AE.

For a combined criterion to be fulfilled, all conditions have to be fulfilled on the same visit. The criteria are not mutually exclusive, e.g., a subject with ALT = 6.42x ULN is counted for ALT > 3x ULN and ALT > 5x ULN.

For urinalysis, all parameters collected will be listed.

## 2.6.4 Other safety data

### 2.6.4.1 Vital signs

Analysis in vital sign measurement using descriptive summary statistics for the change from baseline for visits up to Week 52 will be performed by vital sign parameters and treatment group. Change from baseline will only be summarized for subjects with both baseline and post-baseline values and will be calculated as:

$$\text{change from baseline} = \text{post-baseline value} - \text{baseline value}$$

All vital signs will be listed with “on-treatment” flag displayed. In addition, Box and Whisker plots of hematology and serum chemistry will be provided for absolute values over time for Treatment period 1 and Entire study period.

The number and percentage of subjects with newly occurring notable vital signs will be presented. Criteria for notable vital sign abnormalities are provided in [Table 2-6](#) below.

**Table 2-6 Criteria for notable vital sign abnormalities**

Vital sign (unit)	Notable abnormalities
Systolic blood pressure (mmHg)	$\geq 140$ mmHg or $< 90$ mmHg
Diastolic blood pressure (mmHg)	$\geq 90$ mmHg or $< 60$ mmHg
Pulse (bpm)	$> 100$ bpm or $< 60$ bpm

## **2.7 Pharmacokinetic endpoints**

All subjects with quantifiable pharmacokinetic (PK) measurements of secukinumab will be included in the pharmacokinetic data analysis.

Serum concentrations will be expressed in mass per volume units. All concentrations below the limit of quantification as well as missing data will be labeled as such in the concentration data listings.

PK concentrations will be summarized by analysis visit and treatment group. In addition to mean, standard deviation (SD), coefficient of variation (CV), median and quartiles, the geometric mean and geometric coefficient of variation (CV) and n(log) will be presented. The formula for deriving the geometric mean and CV (%) is as following:

- CV (%) =  $(SD/\text{mean}) * 100$ ,
- geometric mean =  $\exp(\text{sum of log transformed data}) / \text{number of non-missing data points after log transformation}$ ,
- geometric CV =  $\sqrt{\exp(\text{variance of log-transformed data}) - 1} * 100$ .
- n(log) = number of non-missing data points after log transformation

In addition, sample number, concentration, sample date, sample time at pre-dose and minutes pre-dose will be listed by treatment sequence.

Values below lower limit of quantification/below detection limit will be imputed by 0.

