Subjects who discontinue study treatment will continue to be followed up for as long as possible, and efforts should be made so that subjects continue study visits as per the assessment schedule even if not on study drug. Special effort should be made up until Week 16 to ensure that those subjects who prematurely discontinue study treatment attend all scheduled visits.

Subjects who discontinue study treatment before completing the study and do not wish to attend site visits for assessments only should be scheduled for an end of study visit 2 weeks (whenever possible) after their last study treatment administration, at which time all the assessments listed for EOT 1 (Week 16)/EOT 2 (Week 52) will be performed. Subjects should then return to the study site 8 weeks after completing EOT visit at Week 60 Follow-Up visit for final safety and efficacy assessments.

If a subject refuses to return for these assessments or are unable to do so, every effort should be made to contact them or a knowledgeable informant by telephone or by sending appropriate correspondence (i.e. certified letter) immediately. At this contact, the safety (e.g., potential occurrence of AE or SAE) and the primary reason for a subject’s premature withdrawal should be determined.

At a minimum, subjects who pre-maturely discontinue the treatment will be contacted for safety evaluations during the 10 weeks following the last dose of study treatment, including final

contact at the 10 week point. Documentation of attempts to contact the subject should be recorded in the subject record.

It is recommended that assessments be completed in the following order: PROs, Physician assessments, study visit procedures (e.g. laboratory and PK sample collection, vital signs measurements), study treatment administration.

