12.5.3 Pharmacokinetics

PK concentrations will be listed by treatment and subject and Cmin will be determined. Descriptive summary statistics will include mean (arithmetic and geometric), SD, and CV (arithmetic and geometric), median, minimum and maximum.

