16.2 Appendix 2: Blood samples collection

Table 16-1 Blood log: Time schedule for blood sampling

Period	Visit Name	Hematology	Clinical Chemistry	Serum pregnancy test	Blood sample for PK		Blood sample for IG		Biomarker	TB test	Total volume (ml)
		Volume (ml)	Volume (ml)	Volume (ml)	Dose Ref. ID#	Volume (ml)	Volume (ml)	Volume (ml)	Volume (ml)	Volume (ml)	
Screening	Screening 1	4.8	3.5	2						4	14.3
	Screening 2										0
Treatment Period 1	Baseline	4.8	5		1	2	2	15			28.8*
	Week 1										0
	Week 2	4.8	3.5								8.3
	Week 3										0
	Week 4	4.8	3.5								8.3
	Week 8	4.8	3.5								8.3
	Week 12	4.8	3.5								8.3
	Week 16/EOT1	4.8	5		2	2	2	15			28.8
Treatment Period 2	Week 17										0
	Week 18	4.8	3.5								8.3
	Week 19										0
	Week 20	4.8	3.5								8.3
	Week 24				3	2					2
	Week 28	4.8	3.5								8.3
	Week 32										0
	Week 36										0
	Week 40										0
	Week 44	4.8	3.5								8.3
	Week 48										0
	Week 52/EOT2	4.8	5		4	2	2	15	4		32.8

Period	Visit Name	Hematology	Clinical Chemistry	Serum pregnancy test	Blood sample for PK		Blood sample for IG	Biomarker	TB test	Total volume (ml)
		Volume (ml)	Volume (ml)	Volume (ml)	Dose Ref. ID [#]	Volume (ml)	Volume (ml)	Volume (ml)	Volume (ml)	
Post-Treatment Follow-Up	Week 60	4.8	3.5		4	2	2			12.3

* For patients who sign optional DNA sampling ICF, 3 ml of blood will be additionally collected at baseline visit. # Dose reference IDs 1, 2 and 3 are collected pre-dose; scheduled post-dose time points for dose reference ID 4 are collected 2 and 10 weeks post-last study dose.

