#### **2.5.1.1 Visit windows**

Visit windows will be used for the data that is summarized by visit. They are based on the study evaluation schedule and comprise a set of days around the nominal visit day. For any assessment, there are the protocol defined scheduled visits around which visit windows were created to cover the complete range of days within the study. For subjects randomized to Placebo to secukinumab 300 mg every 2 weeks arm and Placebo to secukinumab 300 mg every 4 weeks arm, the day of taking the first secukinumab dose will also need to be taken into visit window consideration. Further information will be found in Study Programming Dataset Specifications (PDS). The visit windows are shown in [Table 2-1](#). In these tables, the days are counted since the first dose of study treatment (study day 1). These visit windows apply to measurements taken at every visit. For assessments collected less often different visit windows will be applied as detailed below.

When visit windows are used, all visits will be re-aligned, i.e. they will be mapped into one of the visit windows. E.g., if the Week 4 visit of a subject is delayed and occurs on Day 60 instead of on Day 29, it will be re-aligned to visit window Week 8. In the case of major deviations from the visit schedule, or due to unscheduled visits, several assessments of a subject may fall in a

particular visit window (either scheduled or unscheduled). Statistical approaches to handle multiple assessments in a given visit window are specified below.

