**Table 2-1 Assessment windows for scheduled visits for analyses based on the entire study period**

Analysis Visit	Week	Scheduled Day	Visit Window
Baseline	BSL	1	-28 days to Day 1*
Week 1	1	8	Day 2-11
Week 2	2	15	Day 12-18
Week 3	3	22	Day 19-25
Week 4	4	29	Day 26-43
Week 8	8	57	Day 44-71
Week 12	12	85	Day 72-99
Week 16	16	113	Day 100-120
Week 18	18	127	Day 121-134
Week 20	20	141	Day 135-155
Week 24	24	169	Day 156-183
Week 28	28	197	Day 184-211
Week 32	32	225	Day 212-239
Week 36	36	253	Day 240-267
Week 40	40	281	Day 268-295
Week 44	44	309	Day 296-323
Week 48	48	337	Day 324-351
Week 52	52	365	Day 352-379
Follow up	60	421	Starting from day 380

\* Baseline measurement before the first drug administration.

For HiSCR, HiSCR components inflammatory nodules, abscesses, draining fistulae, Flare and other lesion related assessments, Screening 1 visit, Screening 2 visit and baseline visit will be adjusted per below table

Analysis Visit	Week	Scheduled Day	Visit Window
Screening 1	-4	-21	-28 days to -14 days
Screening 2	-2	-7	-13 days to -1 days
Baseline	BSL	1	Day 1

For parameters which are not collected at every visit (e.g. weight, laboratory parameters, DLQI), visit windows defined in and [Table 2-1](#) will be combined. The following rules are used to determine the visit window for an applicable visit post baseline: “Lower limit” = “upper limit of prior applicable visit” + 1. “Upper limit” = “target day of current visit” + integer part of (“target day of next applicable visit” – “target day of current visit”)/2. For example, if a parameter is measured at Baseline, Week 12 and Week 28 only, Week 12 visit window will extend from Day 2 to Day 141 (combining Week 1 to Week 20 visit windows), Week 28 will extend from Day 142 to Day 379 (combining Week 24 to Week 52). If more than one assessment falls into the interval, the rules defined below are applied.

The analysis visit will be used for listing of visit and period for both safety and efficacy data. If a visit falls after the last visit window (after Day 379) it is not assigned to an analysis visit and will be listed under label “After Week 52”.

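### SAP 2.7 summarises PK by study-day window with no limit on time since last dose, so some 10-week post-treatment samples are reported as Week 16, 24 or 52 concentrations

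*SAP*

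**What the plan says.** SAP Section 2.7 sets the unit of summary ("PK concentrations will be summarized by analysis visit and treatment group") and the population ("All subjects with quantifiable pharmacokinetic (PK) measurements of secukinumab will be included in the pharmacokinetic data analysis"). The inclusion rule works at subject level; no sample is excluded or relabelled by its distance from the last dose.

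SAP Section 2.5.1.1 defines analysis visits by study day and overrides the nominal label: "When visit windows are used, all visits will be re-aligned, i.e. they will be mapped into one of the visit windows". For sparsely collected measures ("For parameters which are not collected at every visit (e.g. weight, laboratory parameters, DLQI), visit windows defined" in Table 2-1) the windows are combined by formula. Section 2.5.1.2 and Table 2-2 keep the value closest to the scheduled day, and the earlier one on a tie. Follow-up begins only at Day 380, whenever treatment stopped.

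Protocol Table 16-1 schedules PK at Baseline and Weeks 16, 24, 52 and 60. Its footnote reads: "scheduled post-dose time points for dose reference ID 4 are collected 2 and 10 weeks post-last study dose". Protocol Section 8 gives discontinuers who do not want to keep attending an end-of-treatment (EOT) visit about 2 weeks after the last dose, and then: "Subjects should then return to the study site 8 weeks after completing EOT visit at Week 60 Follow-Up visit". The purpose of the PK data is in Protocol Section 12.5.3: "PK concentrations will be listed by treatment and subject and Cmin will be determined".

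**The concern.** A concentration shown under Week 16, 24 or 52 will be read as the level reached on the regimen at that time, the more so because the protocol wants Cmin and the samples up to Week 24 are drawn before dosing. The windows look only at days since the first dose. A sample taken 10 weeks after treatment stopped can therefore fall in a treatment-period window and be chosen to represent the patient there. Discontinuers who stay in the study, as the protocol asks, also contribute off-drug samples, and these enter at their true nominal visits.

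At stake is the description of exposure on the two regimens. Protocol Section 4.2 justifies the q2w arm by the higher exposure it should give, so readers will set the two columns side by side. The distortion depends on when and how often patients stop, which may differ between arms.

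**Working it through.** **Inputs.** PK visits: Protocol Table 16-1. Target days 113, 169, 365 and 421 for Weeks 16, 24, 52 and 60: SAP Table 2-1. Window formula: SAP 2.5.1.1. Selection rule: SAP 2.5.1.2. EOT at last dose + 14 days and F8 at last dose + 70 days: Protocol Section 8 and the Table 16-1 footnote.

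**1. Reproduce the SAP's example.** Upper limit = target + integer part of half the gap to the next target; lower limit = previous upper limit + 1. For a measure taken at Baseline, Week 12 and Week 28, the Week 12 upper limit is 85 + (197 − 85)/2 = 141. This gives Day 2–141 and then Day 142–379, as the SAP states.

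**2. Apply it to PK.**
- Week 16: 113 + (169 − 113)/2 = 141, so Day 2–141.
- Week 24: 169 + (365 − 169)/2 = 267, so Day 142–267.
- Week 52: the formula alone gives 365 + (421 − 365)/2 = 393, but Table 2-1 closes Week 52 at Day 379. I use Day 268–379; the counts below are the same with 393.

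**3. Enumerate.** There are 29 scheduled injection days before Week 50. I took each as the last dose of a patient who then attends only EOT and F8. Scheduled Day 113 and Day 169 samples are included if the patient was dosed on or after that day.

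| Last dose | Study days | F8 sample reported as | Dosing days |
|---|---|---|---|
| Weeks 0–8 | 1–57 | Week 16 | 7 |
| Week 10 | 71 | not selected (tie; EOT used) | 1 |
| Weeks 12–18 | 85–127 | Week 24 | 5 |
| Weeks 19–28 | 134–197 | not selected (EOT or scheduled sample closer) | 6 |
| Weeks 30–44 | 211–309 | Week 52 | 8 |
| Weeks 46–48 | 323–337 | not at a treatment visit | 2 |

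Total: 7 + 5 + 8 = 20 of 29. Example: last dose Week 40 (Day 281) gives EOT on Day 295, 70 days from the Week 52 target, and F8 on Day 351, 14 days from it; F8 is kept. A last dose on Day 43, 99 or 295 puts F8 exactly on the target day of Week 16, 24 or 52.

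**4. Vary the window reading.** The SAP describes Day 2–141 as combining Weeks 1 to 20, although Table 2-1 ends Week 20 at Day 155; ending the Week 16 PK window there gives 21 of 29. With uncombined Table 2-1 windows, only last doses on Days 43, 99, 113, 295 and 309 put F8 under Week 16, 24 or 52: 5 of 29.

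**5. Look for a safeguard.**
- The SAP 2.6 on-treatment limit is last dose + 84 days and is written for safety data. Since 70 < 84, it would not remove F8 in any case.
- Weeks 52 and 60 share dose reference ID 4, so the ID does not separate them.
- The limits of 4 and 12 weeks since last dosing in SAP 2.5.1.1 apply only to patients who used the pandemic unscheduled visits.

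**6. Size, under assumptions.** The documents give neither a half-life nor a discontinuation rate. Assume a half-life h of 20–35 days and that a fraction f of 5–10% of a visit's values are F8 samples. For q2w, the ratio of an F8 value to a 14-day value is r = 2^(−56/h): 0.14 at h = 20 and 0.33 at h = 35. The geometric mean falls by 1 − r^f and the arithmetic mean by f(1 − r).

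| q2w | h = 20 | h = 35 |
|---|---|---|
| Geometric mean, f = 5% | −9.2% | −5.4% |
| Geometric mean, f = 10% | −17.6% | −10.5% |
| Arithmetic mean, f = 5% | −4.3% | −3.4% |
| Arithmetic mean, f = 10% | −8.6% | −6.7% |

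For q4w, r = 2^(−42/h), or 0.23–0.44, and the geometric mean falls by about 4–14% over the same ranges.

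**The case against.** The strongest reply is that few patients meet the conditions. A patient must stop treatment, stop scheduled visits, still attend both EOT and F8, and have a last dose in one of three ranges. If stops are spread evenly over 50 weeks, Weeks 30–44 cover 16/50 = 0.32 of the time and Weeks 30–48 cover 0.40. With 26% discontinuing, all in this way, F8 samples are 0.26 × 0.32 / (0.74 + 0.26 × 0.40) ≈ 10% of Week 52 values. With 15% discontinuing and half doing so, the share is 0.075 × 0.32 / (0.85 + 0.075 × 0.40) ≈ 3%, or about 4% on the q2w geometric mean at a 27-day half-life. This limits the size; it does not remove the mislabelling.

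A reader might also infer that reported concentrations can only be too low. The documents do not support that. Scheduled q4w samples at Weeks 16, 24 and 52 come 4 weeks after an active dose, so a q4w EOT sample taken 2 weeks after an active dose can raise the summary. Placebo patients who stop before Week 16 have no secukinumab to wash out. Values below quantification are set to 0, so they lower the arithmetic mean but drop out of the log-scale statistics.

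It is also fair that PK is not named among the SAP's combined-window examples, that further window detail is deferred to a programming specification not available here, that medians and quartiles are reported too, and that sample dates are listed. SAP 2.7 itself never calls these values troughs; that reading comes from the visit labels and the protocol's Cmin. The listings let a reader find the samples, but the summary table would still include them.

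**Conclusion.** The point holds as a limited defect in an analysis rule. Read as written, the SAP reports a 10-week post-treatment sample as a Week 16, 24 or 52 concentration for 20 of 29 possible last-dose days among discontinuers who attend only EOT and F8, and for 5 of 29 if windows are not combined. Off-drug samples from discontinuers who keep attending enter as well, by their nominal visit rather than by windowing.

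It would go too far to say that all early discontinuers' washout samples are counted as on-treatment values, or that the plan understates exposure by a known amount. The effect depends on the last-dose day and on attendance. The 5–18% range for the q2w geometric mean rests on an assumed half-life, an assumed share of affected values, log-linear decline, and a 14-day value equal to that of patients who stay on treatment. That last assumption is doubtful for last doses in or just after the weekly induction. The summary is exploratory and descriptive; neither the primary nor the secondary tests use it. The change is worth making because the protocol wants Cmin and the correction is cheap.

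**What to change.** In SAP Section 2.7, state that the study-day windows do not apply to PK. Summarise Weeks 16, 24 and 52 by nominal scheduled visit, using only samples from patients still on treatment and taken at about the regimen's planned interval after the last active dose, within a tolerance given in the text. The time-since-dose condition is needed as well as the nominal label, because relabelling alone would leave in the off-drug samples of discontinuers who keep attending. Report discontinuers' EOT samples, all F8 samples and other off-treatment samples in separate rows by time since the last secukinumab injection, so that placebo injections in the q4w arm do not reset the clock.

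No new data are needed: doses are recorded under Protocol Section 6.6.1 and sampling dates and times under Section 8.5.2. The cost is a few lines of SAP text, some programming, and a slightly smaller n in the by-visit table.

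### The SAP's geometric mean formula for PK concentrations divides outside the exponential, so it gives the product of the values divided by n

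*SAP*

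**What the plan says.** Protocol Section 12.5.3 lists the PK summaries: "Descriptive summary statistics will include mean (arithmetic and geometric), SD, and CV (arithmetic and geometric), median, minimum and maximum". It gives no formula for any of them.

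SAP Section 2.7 puts this into operation. It says that "PK concentrations will be summarized by analysis visit and treatment group" and introduces its bullet list with "The formula for deriving the geometric mean and CV (%) is as following". The bullets are therefore the derivation rule. In the text's formula mark-up, the geometric mean bullet reads "\exp(\text{sum of log transformed data}) / \text{number of non-missing data points after log transformation". The bracket after the exponential closes before the division sign.

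The divisor is the quantity that the last bullet of the list names n(log), the "number of non-missing data points after log transformation". The geometric CV bullet is built on the "variance of log-transformed data" and has the standard form, √(exp(variance of logs) − 1) × 100.

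No other section of either document gives a geometric mean formula. SAP Section 4, on changes from the protocol, mentions only the HS-PGA response definition, so no deliberate departure is declared.

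**The concern.** A geometric mean is the exponential of the average log. Here the sum of the logs is exponentiated before any averaging, and the division comes afterwards on the raw scale. The result is the product of all concentrations divided by their number.

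The units also show the fault. Section 2.7 expresses serum concentrations as mass per volume. The product of n concentrations has units of (mass/volume) to the power n, so the printed expression cannot be a concentration.

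A formula in a SAP is a specification for the production program and for any independent validation program. If it is coded literally, the geometric means for the two regimens are unusable. If programmers quietly use the right formula, the SAP no longer describes what was done. The statistic has some interest here because Protocol Section 4.2 justifies the every-2-weeks regimen by the higher exposure it is expected to give.

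**Working it through.** The documents report no geometric mean, so there is no figure of theirs to reproduce. The check evaluates the printed expression and compares it with the correct one. All concentrations below are illustrative assumptions.

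**Inputs from SAP Section 2.7**

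- Printed rule: exp(Σ log x) / n, with n = n(log).
- Values below quantification: "Values below lower limit of quantification/below detection limit will be imputed by 0". A zero has no log, so these values drop out of both the sum and n(log).

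**Algebra**

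- exp(Σ log x) = x₁ × x₂ × … × xₙ, so the printed rule equals (product of the values) / n.
- The geometric mean is GM = exp(Σ log x / n) = (product)^(1/n).
- Hence printed value = GMⁿ / n. This equals GM when n = 1. For n > 1 it does so only by coincidence, when GM^(n−1) = n.

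**Numbers**

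| Values | Printed rule | Geometric mean |
|---|---|---|
| 40, 50, 60 | 120,000 / 3 = 40,000 | 120,000^(1/3) = 49.3 |
| 20, 40 | 800 / 2 = 400 | 28.28 |
| 20, 40, 80 | 64,000 / 3 = 21,333 | 40.0 |
| 30, 45, 60, 75, 90 | 546,750,000 / 5 = 109,350,000 | 55.92 |
| 1, 1, 1, 1 | 1 / 4 = 0.25 | 1 |
| 0.02, 0.04, 0.08 | 0.000064 / 3 = 0.0000213 | 0.040 |

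**Dependence on the unit.** The sixth row is the third row divided by 1,000. The geometric mean falls by a factor of 1,000, as it should. The printed value falls by 1,000³ = 10⁹.

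**Dependence on group size.** Suppose every value is 50. With n = 2 the printed rule gives 2,500/2 = 1,250. With n = 3 it gives 125,000/3 = 41,667. The geometric mean is 50 in both cases. Two groups with identical exposure would therefore differ merely because one has an extra sample.

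**Realistic size.** About 180 patients are planned per secukinumab arm (Protocol Section 3). With 180 values of 50, log₁₀ of the printed result is 180 × log₁₀(50) − log₁₀(180) = 305.81 − 2.26 = 303.6. The result is about 10^303.6, against a geometric mean of 50.

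**After correction.** With the division inside the exponential, a standard library geometric mean function returned the same values as the right-hand column for every row from the second down. The first row follows directly from its cube root.

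**The case against.** Three points can be made on the other side.

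First, the whole error is the position of one bracket. If the original page uses a stacked fraction or an outer bracket, conversion from PDF could have flattened it into this form. That cannot be excluded entirely, and the page should be checked. However, the geometric CV formula in the same list came through with its nested brackets correct, and nothing else there looks corrupted.

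Second, the practical risk is low. The geometric mean is a standard quantity, the analysis uses SAS (SAP Section 2.1), and the SAP names the right ingredients. A literal result would be so extreme at real group sizes that it would very probably be noticed. The arithmetic mean, median and quartiles are reported alongside, so exposure could still be read. This stands and limits the importance of the point. It does not make the formula right.

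Third, nothing inferential depends on it. PK is an exploratory objective, PK/PD analysis is reported separately (SAP Section 2.8), and no hypothesis, alpha level or sample size uses the geometric mean. This also stands.

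**Conclusion.** The formula is wrong as written. For more than one value it generally does not return a geometric mean. It returns the n-th power of the geometric mean divided by n, in the wrong units: 40,000 instead of 49.3 in the three-value example. The algebra holds for any positive data and needs no assumption about the trial. Only the example concentrations are assumed.

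The one reservation is that the bracket in the original PDF should be confirmed. The fault is confined to one bullet in SAP Section 2.7. The protocol text does not contain it, and the neighbouring CV formulas are sound. This is a minor correction to a required descriptive summary, with no bearing on the primary or secondary conclusions.

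**What to change.** Check the original page. If the bracket stands as printed, replace the bullet in SAP Section 2.7 with:

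geometric mean = exp[(sum of log-transformed concentrations) / n(log)]

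where n(log) keeps its present definition. Confirm that the production and validation programs for the PK summary tables use this form.

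The cost is one moved bracket. Design, data collection, sample size and testing are unchanged, and the protocol needs no amendment because Section 12.5.3 gives no formula.
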